3.1.1. Study Sample

Patient inclusion and exclusion criteria can be found in Sections 8.1 and 8.2 of the protocol.

3.1.2. Treatment Arms

This is a single-arm study. All patients will be treated with study drug rFVIII Fc.

Within this single arm, there are 3 possible treatment regimens: An optional episodic (on-demand) regimen; a required prophylactic regimen for all patients; and an ITI regimen available only for patients who develop an inhibitor as defined in Section 3.1.2.3.

3.1.2.1. Episodic Treatment Regimen

The episodic (on-demand) regimen is optional in this study, and, if implemented, must precede initiation of the prophylactic treatment regimen. Dosing and duration of episodic treatment is determined by the Investigator. Date of transition from episodic treatment to prophylactic treatment is captured on the study electronic case report form (eCRF).

3.1.2.2. Prophylactic Treatment Regimen

The use of a prophylactic treatment regimen in young children, which is the target population in this study, is currently the recommended standard of care in hemophilia due to the demonstrated

benefit on long-term outcomes. It is anticipated that patients will begin a prophylactic treatment regimen prior to or immediately following the occurrence of a third hemarthrosis (joint bleed).

The dose for initiation of prophylaxis may be chosen by the Investigator within the range of 25 to 80 IU/kg. Treatment continues until the patient reaches at least 50 EDs to study drug, or completes follow-up of an ITI regimen (if applicable), or the end of study is declared by Bioverativ.

3.1.2.3. Immune Tolerance Induction (ITI) Treatment Regimen

After exposure to rFVIII Fc, any patient who develops a positive high-titer inhibitor or a positive low-titer inhibitor (both defined in Section 5.1.2.4) with poorly controlled bleeding, is eligible to undergo an ITI regimen with rFVIII Fc. The ITI treatment regimen consists of single injections of rFVIII Fc 200 IU/kg/day, consistent with current ITI guidelines.² Duration of ITI treatment is up to 33 months, followed by a tapering off regimen of at least 3 months (12 weeks). Separate consent is required before starting an ITI treatment regimen.

3.1.3. Procedures for Discontinuing Treatment and Removal of Patients from the Study

The parent/legal guardian may withdraw the patient from the study, or the patient may withdraw from the study, at will at any time. A patient must discontinue study treatment and be withdrawn from the study for any of the following reasons:

- The patient is found to have a factor VIII (FVIII) activity $\geq 1\%$ or a positive inhibitor based on central laboratory results obtained during the Screening Period.
- The patient develops a positive inhibitor following enrollment and is eligible for ITI AND opts not to undergo or continue ITI.
- A patient who is in the tapering period (or the subsequent follow-up monitoring period) of the ITI treatment regimen and develops inhibitors (that is, had a relapse).
- The patient develops a \geq Grade 2 allergic drug reaction in association with the administration of rFVIII Fc, as defined by the Recommendations for Grading of Acute and Subacute Toxic Effects on the World Health Organization (WHO) scale:³
 - Grade 2: bronchospasm; no parenteral therapy needed
 - Grade 3: bronchospasm; parenteral therapy required
 - Grade 4: anaphylaxis
- The patient uses FVIII products other than rFVIII Fc (exception allowed for 1 emergency or accidental use).
- The patient receives concomitant immunomodulation.
- The patient develops any condition that precludes him from complying with the study procedures.

- The patient experiences a medical emergency that necessitates discontinuation of treatment.
- It is not in the patient's best interest to continue with the study treatment, in the judgment of the Investigator.
- The parent/legal guardian decides to withdraw the patient from the study.

At the discretion of the Investigator, a patient may be withdrawn due to noncompliance.

The reason for the patient's withdrawal from the study must be recorded in the patient's eCRF.

For any patient who is not responding to treatment with rFVIII Fc, as determined by the Investigator, a decision will be made with the Bioverativ Medical Monitor whether to continue the patient in the study.

3.1.4. End of Study

End of the study (EOS) will occur after at least 90 patients have reached at least 50 EDs with rFVIII Fc.

3.1.5. Dose Adjustments

All bleeding episodes are to be treated with study drug. The dose to treat the bleeding episode will be based on the patient's clinical condition, known PK information, type and severity of the bleeding episode, and input from the Medical Monitor, if necessary.

3.1.5.1. Episodic Treatment Dose Adjustment

The Investigator has the option to treat the patient episodically, starting after the confirmation of eligibility and lasting until a prophylactic treatment regimen is initiated. Dosing will be determined by the Investigator using the guidelines in [Appendix A](#) of the approved study protocol.

3.1.5.2. Prophylactic Treatment Dose Adjustment

The dose for initiation of prophylaxis may be chosen by the Investigator within the range of 25 to 80 IU/kg. The dose can be adjusted based on the patient's response to dosing in the range of 25 to 65 IU/kg at 3- to 5-day intervals. Adjustments to the dose and dosing interval can be made based upon available IR data, subsequent FVIII activity levels, level of physical activity, and bleeding pattern, in accordance with local standards of care for a prophylactic treatment regimen.

3.1.5.3. Immune Tolerance Induction (ITI) Dose Adjustment

An ITI regimen comprises of high daily doses of replacement factor. Therefore regimen in this study approximates the high-dose treatment arm of the International ITI Study protocol, and utilizes single injections of rFVIII Fc of 200 IU/kg/day. After a maximum of 33 months of ITI, the administered dose will be tapered off as follows:

- [REDACTED]
- [REDACTED]

After this tapering period, the patient reverts to a prophylactic treatment regimen for the relapse monitoring period. See Section 7.4.9 for further details.

3.1.6. Independent Data Monitoring Committee

An independent, external Data Safety Monitoring Committee (DSMC) is responsible for evaluating and monitoring the safety and tolerability of the study drug on an ongoing basis during the study. The specifics regarding the DSMC organization and procedures is outlined in the DSMC Charter.

3.2. Statistical Hypothesis

There is no statistical hypothesis for this study as all but the primary endpoint will be analyzed descriptively only. The methodology for analysis of the primary endpoint is described in Section 9.4.3.

3.3. Sample Size Justification

The planned total sample size for this study is approximately 105 patients.

Because the size of the hemophilia population is limited, the sample size is based on clinical rather than statistical considerations. Taking into account the CHMP Guideline¹ and in an effort to enroll a sufficient number of patients to assess the efficacy and safety of rFVIII Fc in this population of primarily very young children, approximately 105 patients will be dosed with rFVIII Fc to achieve at least 90 patients with at least 50 EDs by the completion of the study.

3.4. Randomisation and Blinding

This is an open-label single arm study so there is no blinding or randomization.

3.5. Interim Analysis

There will be one interim analysis, performed when the study milestone of at least 50 patients with 50 EDs is reached and the 50 ED inhibitor tests for all patients who reach this milestone have been performed and have present and valid results. Except where indicated, the analyses described in this plan will be performed for both the interim and final analyses.

4. ANALYSIS POPULATIONS

By definition, the patients included in these population sets will differ between the interim and final analyses.

4.1. All-Enrolled Analysis Set

The All-Enrolled Analysis Set is defined as all patients who were enrolled in the study, whether dosed with rFVIIIIFc or not. Patients will be considered enrolled when the Investigator has verified that they are eligible according to the criteria in [Sections 8.1, 8.2 and 8.3](#) of the protocol.

Patient disposition summaries, enrollment summaries and all patient data listings will be based on the All-Enrolled Analysis Set, unless otherwise stated in this SAP.

4.2. Safety Analysis Set

The Safety Analysis Set is defined as all patients who received at least 1 dose of study rFVIIIIFc. All analyses and summaries of safety, demographics, and baseline characteristics will be based on the Safety Analysis Set, unless otherwise specified in this SAP.

4.3. Full Analysis Set

The Full Analysis Set (FAS) is defined as all enrolled patients who receive at least 1 dose of study rFVIIIIFc. All analyses and summaries of efficacy and exploratory endpoints will be based on the FAS, unless otherwise specified in this SAP.

4.4. ITI Analysis Set

The ITI Analysis Set is defined as all patients who consent to and initiate the ITI sub-study (see [Section 3.1.2.3](#)). All analyses and listings of data from the ITI sub-study will be presented for this population.

5. DEFINITIONS AND DATA HANDLING

Study 997HA306 is being conducted under the sponsorship of Bioverativ Therapeutics Inc. Data management is being performed under contract with Quintiles in collaboration with Bioverativ. Statistical analysis will be performed by Bioverativ's Biostatistics Department and/or a designated contract research organization (CRO), using SAS® version 9.4 or higher and, where appropriate, additional validated software. This SAP is based on Version 6 of the approved study protocol dated 12 February 2018 and details the analyses to be performed and summaries to be produced for the interim and final analyses for the Clinical Study Report(s) (CSRs).

5.1. General Principles

In general, the following approaches will be used in analysis/summary of baseline/demography, safety, efficacy and exploratory endpoint data, unless otherwise specified in this SAP.

Data will be summarized using standard summary statistics for continuous and categorical data, as appropriate (additional information is provided in Section 5.3).

No statistical hypothesis testing is planned. However, 95% confidence intervals (CIs) when determined for a binomial proportion will use the Clopper-Pearson method.

5.1.1. Data Presentation

In general, presentations of background/demography and safety data include an overall/total column and those for efficacy and outcome data do not. Any exceptions to this are specified in the relevant section.

5.1.1.1. General

There is only 1 treatment arm in the study. However unless otherwise stated, all analyses and background/demography tables will be presented for the following treatment groups, as defined in Section 3.1.2:

- Patients who were ever on an episodic regimen
- Patients who were ever on a prophylactic regimen
- Patients who were ever on an ITI regimen

For longitudinal data, the safety or efficacy periods included for these groups is the time spent on that regimen within that period. These periods are defined in Section 5.2 and 5.4.

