### **16.2. Efficacy**

#### **16.2.1. Analysis Population**

Subjects who receive at least 1 dose of rFVIIIhFc will be included in the Full Analysis Set (FAS). Efficacy analyses will be based on the FAS, including the data collected on or after the time of the first injection of rFVIIIhFc study drug.

Subjects developing a confirmed positive inhibitor test after exposure to rFVIIIhFc (the Inhibitor Subgroup) will have their efficacy data included up to the time of the last negative inhibitor test; efficacy data collected after the time of the last negative inhibitor test will be summarized separately.

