### **16.5. Safety**

Unless specified otherwise in the SAP, safety data will be summarized overall. Subjects developing a confirmed positive inhibitor test after exposure to rFVIII Fc study drug (the Inhibitor Subgroup) will have their safety data included up to the time of the last negative inhibitor test; safety data collected after the time of the last negative inhibitor test will be summarized separately.

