5.1.1.2. Inhibitor Subgroups

Selected tables will further be presented by the following groups:

- Patients in the inhibitor subgroup (see Section 5.1.2.5)
- Patients not in the inhibitor subgroup

For longitudinal data, the safety or efficacy periods included for these groups is the entire period, again as described in Section 5.4.

Patients in the inhibitor subgroup will be further split by the sub-classification of inhibitor as described in Section 5.1.2.5, namely:

- Patients with high-titer inhibitors
- Patients with low-titer inhibitors that meet the clinically meaningful criteria as defined in Section 5.1.2.5
- Patients with low-titer inhibitors that do not meet the clinically meaningful criteria

For this presentation, the analysis of longitudinal data will be presented for the entire safety or efficacy periods, dichotomized as described in Section 5.4.7, i.e.:

- From start of the relevant period up to the date of the positive inhibitor (all patients in the inhibitor subgroup combined)
- From date of positive inhibitor to the end of the relevant period

The definition of a positive inhibitor and the date of onset are described in Section 5.1.2.4.

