5.4.7. Inhibitor Period

For patients who develop inhibitors, safety and efficacy data analysis will be dichotomized into periods before and after this event. The date of the inhibitor, that is, the date of the first sample with a positive test result (subsequently confirmed, see Section 5.1.2.4) will be leveraged for this purpose. The start and end of the inhibitor period are the start and end the relevant period, as defined in Sections 5.4.2 and Section 5.4.4.

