7. EFFICACY ANALYSIS

7.1. General Efficacy Principles

Efficacy analyses will be based on the Full Analysis Set and unless otherwise specified, presented by the treatment regimen groups described in Section 5.1.1.1.

Additionally, the general efficacy and surgical/rehabilitation periods are defined in Section 5.4. Data on bleeding and rFVIIIFc consumption will be based on the efficacy period; surgical evaluations will be based on the surgical/rehabilitation period.

Analysis of efficacy endpoints that are visit-based will include data from all study visits whether or not in the efficacy period, unless that visit is coincidental with a surgical/rehabilitation period for a major surgery, in which case it would be excluded.

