9. SAFETY ANALYSIS

9.1. General Safety Principles

Safety analyses will be based on the Safety Analysis Set and unless otherwise specified, presented by the treatment regimen groups described in Section 5.1.1.1 .

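### The SAP's default by-regimen tables are defined without the protocol's cut at the last negative inhibitor test; the SAP is ambiguous on the point, and Section 10 does not declare the change

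*SAP*

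**What the plan says.** **Protocol.** Section 16.2.1 says that subjects with a confirmed positive inhibitor after exposure "will have their efficacy data included up to the time of the last negative inhibitor test". Section 16.5 has the same rule for safety: they "will have their safety data included up to the time of the last negative inhibitor test". Both sections send later data to a separate summary, and the synopsis repeats the rule.

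**SAP default.** Section 5.1.1.1 forms three groups (ever on an episodic, prophylactic or ITI regimen) and states that "the safety or efficacy periods included for these groups is the time spent on that regimen within that period". It points to Sections 5.2 and 5.4 for the periods. Section 7.1 has efficacy results "presented by the treatment regimen groups described in Section 5.1.1.1". Section 9.1 reads "Safety analyses will be based on the Safety Analysis Set and unless otherwise specified, presented by the treatment regimen groups". Section 5.1.1 adds that, in general, "presentations of background/demography and safety data include an overall/total column".

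**SAP on inhibitors.** Section 5.4.7 says that for inhibitor patients "safety and efficacy data analysis will be dichotomized into periods before and after this event", dividing at the first positive sample that was later confirmed (defined in 5.1.2.4). Section 5.1.1.2 gives the inhibitor yes/no tables the whole period. It puts the split in the finer sub-classification presentation, whose first part runs "From start of the relevant period up to the date of the positive inhibitor".

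**Declared changes.** Section 10 lists three major differences from the protocol: the FAS definition, the new ITI set and period, and the health outcomes questionnaire. The inhibitor cut is not among them.

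**The concern.** The protocol's rule keeps the main results about treatment of children without an inhibitor. Once an inhibitor is present, bleeding, dose and adverse events may all differ, which is why the protocol separates those data. A reader of the main prophylactic or episodic column will assume the protocol's cut applies. If the columns are built from time on regimen alone, they mix pre- and post-inhibitor time.

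The inhibitor tables recover only part of the separation. They are not by regimen, they do not pool never-inhibitor subjects with the pre-inhibitor data of the others, and they use a different cut date. The outputs at stake are annualized bleeding rate (ABR), consumption, dose per bleed and treatment-emergent adverse events (TEAEs).

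**Working it through.** The plan gives no figure to reproduce on this point. The check is a comparison of rules, followed by arithmetic for scale.

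**1. Is there an inhibitor cut in the rules behind 5.1.1.1?**
- SAP 5.2.1-5.2.4 set regimen start, end and duration from doses, regimen changes and, for episodic treatment, the last visit. No inhibitor date is used.
- SAP 5.4.2 makes the efficacy period equal to the regimen duration, adjusted only for surgical/rehabilitation periods (5.4.2.1) and prophylaxis gaps over 28 days (5.4.2.2).
- SAP 5.4.4 builds the safety period by regimen in the same way, through final follow-up.
- SAP 5.4.7 has the general split, which 5.1.1.2 applies to the sub-classification presentation only.
- SAP Section 12 lists the main tables by regimen, by inhibitor subgroup or by sub-classification. No title shows a by-regimen table with a before/after split.

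**2. Routes by which post-inhibitor time enters the episodic or prophylactic columns**
- (a) Low-titer subjects may continue treatment (Protocol 10.2.5.2.1).
- (b) The interval from the last negative test to regimen change or withdrawal stays in the regimen. For prophylaxis efficacy, part of a dosing suspension may be removed by the 28-day rule.
- (c) Tapering and relapse monitoring, if SAP 5.2.3 governs, because it starts the prophylactic regimen at tapering.

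**3. Scale for one affected subject**

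Inputs: inhibitor tests at 5, 10, 20 and 50 EDs (Protocol 4.2.2.2); prophylaxis every 3 to 5 days (Protocol 10.2.3); confirmation after about 2 to 4 weeks (Protocol 10.2.5.1.2); 3 months of tapering plus 9 of monitoring (Protocol 7.3.2). Assumptions: the cut is the last negative test before the first confirmed positive; no test falls between milestones; all EDs are on prophylaxis.

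(a) Low titer, treatment to 50 EDs. Share after cut = (50 - EDs at cut)/50.
- First positive at 10, last negative at 5: 45/50 = 90%.
- First positive at 20, last negative at 10: 40/50 = 80%.
- With the SAP's first-positive date instead: 40/50 = 80% and 30/50 = 60%.

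(b) ITI starting at confirmation. With d days per ED and c days to confirmation, share = (EDs from last negative to first positive × d + c)/(EDs at first positive × d + c).

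| First positive | d=3, c=14 | d=3, c=28 | d=5, c=14 | d=5, c=28 |
|---|---|---|---|---|
| 10 EDs | 29/44 = 65.9% | 43/58 = 74.1% | 39/64 = 60.9% | 53/78 = 67.9% |
| 20 EDs | 44/74 = 59.5% | 58/88 = 65.9% | 64/114 = 56.1% | 78/128 = 60.9% |

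That is 29 to 78 days, or 56% to 74% of pre-ITI prophylaxis time.

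(c) ITI complete success with full follow-up, after 30 days (10 EDs × 3) to 250 days (50 EDs × 5) of earlier prophylaxis, all taken as before the cut and leaving out route (b) time.
- Tapering and monitoring both prophylaxis (5.2.3): 365/615 = 59.3% to 365/395 = 92.4%.
- Monitoring only (3.1.5.3, prophylaxis after tapering): 274/524 = 52.3% to 274/304 = 90.1%.
- Both kept with ITI (5.4.8, ITI period to study end): 0%.

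**4. What the protocol's cut date means.** The protocol does not say which negative test is the last one. ITI successes need two negative titers (Protocol 10.2.7.4.2), and low-titer subjects may remit (SAP 9.4.3.4), so both produce negative tests after the inhibitor. Read literally, the cut could move to the end of follow-up and remove almost all route (c) time. The anchor in step 3 is a sensible reading, but it is an assumption.

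**The case against.** The strongest reply is that SAP 5.1.1.1 refers to Section 5.4, which contains 5.4.7 and its unrestricted statement that inhibitor patients' data are split. This stands in part: the SAP is ambiguous, and a reader who infers that it has no inhibitor split at all goes beyond the text. Even so, 5.1.1.2 attaches the split to one presentation and gives the yes/no tables the entire period. Even a split at 5.4.7's date would not be the protocol's cut. The evidence from Section 12 is titles only; the table shells, which could show another layout, are not in the documents.

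Protocol 16.2.2 leaves the definition of the efficacy period to the SAP. That is real latitude, but it does not cancel the inhibitor rule in 16.2.1. In 16.5 the allowance for the SAP to specify otherwise concerns summarizing overall; the inhibitor sentence after it carries no such condition. Protocol 16.5.2.2 gives latitude only for adverse events during ITI.

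On tapering, a reader might infer a four-way contradiction among SAP 3.1.3, 3.1.5.3, 5.2.3 and 5.4.8. The first two are design text, 5.2.3 is the explicit regimen-change rule, and Section 10 ties the ITI period to the analysis of ITI response. The conflict is mainly 5.2.3 against 5.4.8 and 3.1.5.3, and a clarification resolves it.

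It is also fair that all analyses are descriptive, that on-ITI time has its own column, and that some outputs do separate ITI data: last prescribed dose (6.6.1.5), key visits (6.1), and the PK listings and recovery summary (Section 8).

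**Conclusion.** The point holds and should be fixed. As written, the default by-regimen tables depart from the protocol's cut, the one split that the SAP describes uses a different date, and Section 10 is silent on both. The protocol's own cut date also needs an anchor.

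The shares (80-90%, 56-74%, and about 59-92% under 5.2.3) describe hypothetical single subjects and rest on that anchor and on the stated timing assumptions. A reader might take them as maxima or as trial estimates; they are neither. They shrink with an interim test, the 28-day rule, relapse (Protocol 11) or end of study (Protocol 7.5). They grow with an earlier inhibitor: 15 days of prior prophylaxis (5 EDs × 3) gives 365/380 = 96%, and a direct switch from episodic treatment to ITI, which 5.2.3 allows, gives 100%. Tapering also has a minimum of 12 weeks and may be modified (Protocol 10.2.7.4.2, 10.2.7.5), so follow-up can exceed 365 days.

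A reader might also infer that the main ABR is inflated. The documents give neither the number of affected subjects nor their bleeding rates, so the size and direction of the effect are unknown. Inhibitor incidence, the primary endpoint, is unaffected.

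**What to change.** - In SAP 5.1.1.1, state that the main episodic and prophylactic columns of the ABR, consumption, dose-per-bleed and TEAE tables, and the overall safety column, include inhibitor-subgroup subjects only up to the last negative test before the first positive sample that was subsequently confirmed. Tabulate later data separately.
- Keep the inhibitor event itself in the primary endpoint and in the SAE summaries (Protocol 15.3.2 makes it reportable as an SAE).
- Use one cut date throughout by aligning 5.1.1.2 and 5.4.7 with it. If the sponsor prefers the first-positive date, apply it to the by-regimen columns too and declare it in Section 10.
- State whether 5.2.3 or 5.4.8 governs tapering and monitoring time in the by-regimen tables, and reconcile the wording of 3.1.3 and 3.1.5.3 with it.
- The uncut by-regimen tables may stay as a sensitivity presentation.

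The cost is SAP wording, one derived date per inhibitor subject and a few more outputs; no new data are needed. The downside is less person-time in the main columns.
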